3.0 Hypotheses

3.1 Hypotheses:

1. We hypothesize that dosimetry-guided, individual dosing of ⁹⁰Y-DOTATOC will provide excellent tumor response.
2. We hypothesize that individual, dosimetry-guided dosing of ⁹⁰Y-DOTATOC will provide maximum safe dose to tumor and minimize renal toxicity while limiting renal radiation dose to ≤ 23 Gy.
3. We hypothesize that ⁶⁸Ga-DOTATOC or ⁶⁸Ga-DOTATATE PET/CT will accurately stage extent of disease at study entry and accurately measure response to therapy at six months following last ⁹⁰Y-DOTATOC treatment.
4. We hypothesize that both quantitative PCR and semi-quantitative immunohistochemical analysis of somatostatin receptor 2 (sstr2) expression on the first diagnostic biopsy of neuroendocrine tumor will positively correlate with standard uptake value (SUV) of that subject's first ⁶⁸Ga-DOTATOC or ⁶⁸Ga-DOTATATE PET scan at study entry.

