4.2 Secondary Objectives

1. For those subjects who participated in the Comparator study of ⁶⁸Ga-DOTATOC versus Octreoscan + conventional imaging using high-resolution, contrast-enhanced CT or MRI (IRB# 201212736), the intent is to determine response to therapy of lesions identified by ⁶⁸Ga-DOTATOC PET/CT but not identified on Octreoscan as a confirmatory measure of true positivity of the Ga-68 DOTATOC avid lesion.
2. Determine if Standard Uptake Value (SUV) on initial ⁶⁸Ga-DOTATOC/TATE PET imaging correlates with SSTR2 expression as measured by quantitative messenger RNA (qPCR) or immunohistochemistry (IHC) on the diagnostic biopsy specimen.

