Treatment efficacy, defined as a complete response, partial response or stable disease (CR+PR+SD), is the primary endpoint of interest in this dosimetry-guided Phase II trial. Tumor response will be defined according to RECIST1.1 criteria applied on up to five target lesions (primary tumor if not surgically removed, up to two liver lesions, up to two nodal metastases, metastatic lesion in other organs, such as ovary, breast) that will be quantified and compared between pre-therapy and 3-9 months post-therapy high-resolution, contrast-enhanced CTs. Osseous metastases may be followed as non-target lesions. ⁹⁰Y-DOTATOC will be deemed worthy of further study if its associated response rate is ≥ 0.60 , and clinically uninteresting if its rate is ≤ 0.40 . Enrollment will proceed according to an optimal Simon two-stage study design. Sixteen (16) subjects will be enrolled in the first stage; if 7 or fewer patients respond, the arm will be closed and the treatment ruled clinically uninteresting. Otherwise, an additional 30 subjects will be enrolled. If 24 or more responses are observed in the total of 46 subjects, then the treatment will be ruled worthy of further study. The study design has a probability of early termination equal to 0.72. Power to detect efficacy is 0.80 with a type 1 error rate of

0.05.

Secondary analysis will focus on time to tumor progression and overall survival. The method of Kaplan- Meier will be used to estimate progression and survival rates. Subjects for whom the outcome of interest is not observed at the 6 month follow-up will be treated as censored observations in the survival analysis.

12.2 Primary Objective 2

Adverse events will be recorded and reported in tabular form by type and grade. If four or more subjects experience renal toxicity \geq Grade 4, the radiopharmaceutical will be declared too toxic and the trial will be stopped. If any other irreversible Grade 4 toxicity is observed in four or more subjects, the treatment will be declared too toxic and will be stopped. Adverse events will be graded according to the most recent CTE guidelines.

12.3 Secondary Objective 1

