For subjects who participated in the ^{68}Ga -DOTATOC Comparator trial (IRB # 201212736), the number, size, and location of discordant lesions between ^{68}Ga -DOTATOC PET/CT and Octreoscan will have been tabulated. This analysis will be updated using the results of post- therapy ^{68}Ga -DOTATOC PET/CT for those patients who participated in the comparator study, but only received the initial ^{68}Ga -DOTATOC PET/CT due to progression on the Octreoscan + high-resolution, contrast-enhanced CT. Lesions that were positive on PET, but negative on Octreoscan will be considered true positive if a response to PRRT is documented after either Cycle 1 or at 6-9 month followup following last ^{90}Y -DOTATOC infusion.

For subjects who did not participate in the ^{68}Ga -DOTATOC Comparator trial, all ^{68}Ga -DOTATOC PET/CT scans will be acquired as part of this study; number, size, and location of lesions will be analyzed between first and subsequent ^{68}Ga -DOTATOC PET/CTs.

12.4 Secondary Objective 2

Compare SUVmax between primary tumor, liver lesions, and extra-hepatic lesions with expression levels of sst2 using qRT-PCR and/or receptor IHC from fresh frozen or paraffin-embedded samples where available.

Compare maximum SUVs of primary tumor, liver lesions, and extra-hepatic lesions with expression level of sst2 RNA and IHC on fresh frozen tissue, or paraffin embedded samples (block(s) or 10 unstained slides) to determine whether or not any correlation exists between SUVmax, sst2 expression, or sst2 protein and response to PRRT. The study is expected to delineate whether measurement of sst2 expression by either qRT-PCT or immunohistochemistry at diagnosis can predict response to ^{90}Y -DOTATOC. We will construct a table tabulating SUVmax, level of RNA expression, and IHC level for all lesions biopsied. With 64 subjects the correlation between SUV max, RNA expression and IHC will be determined. Analysis of SUVmax compared with sst2 RNA and receptor protein expression on primary tumor and metastatic lesions will be considered worthy of further study if $> 50\%$ of lesions demonstrate a positive correlation. Tissue will be sent to 3080 Med Lab in University of Iowa Hospital and Clinics for analysis.

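### Section 12.4's verdict rule for the SUV–sst2 comparison cannot be applied as stated, because a single lesion has no correlation (secondary objective only)

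*Combined protocol and SAP*

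**What the plan says.** Section 12.4 (Secondary Objective 2) compares SUVmax with sst2 expression measured by qRT-PCR and by IHC. Three of its statements matter here.

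- The data layout: "We will construct a table tabulating SUVmax, level of RNA expression, and IHC level for all lesions biopsied".
- A planned correlation: "With 64 subjects the correlation between SUV max, RNA expression and IHC will be determined".
- The verdict: the comparison of SUVmax with RNA and with receptor protein is judged to merit more work if more than 50% "of lesions demonstrate a positive correlation".

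The section names no coefficient, per-lesion agreement rule, cut-off, error rate or target correlation. It also hopes to learn "whether measurement of sst2 expression by either qRT-PCT or immunohistochemistry at diagnosis can predict response to" treatment, and attaches no decision rule to that aim.

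On markers, hypothesis 4 in section 3.1 refers to "both quantitative PCR and semi-quantitative immunohistochemical analysis of somatostatin receptor 2 (sstr2) expression on the first diagnostic biopsy". Section 4.2 item 2 refers to "SSTR2 expression as measured by quantitative messenger RNA (qPCR) or immunohistochemistry (IHC) on the diagnostic biopsy specimen". Section 12.4 describes the assays as "using qRT-PCR and/or receptor IHC from fresh frozen or paraffin-embedded samples where available".

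Section 12.3 (Secondary Objective 1) treats a lesion that is PET-positive but Octreoscan-negative as a true positive if it responds to PRRT, either after Cycle 1 or at the 6–9 month visit. It does not say what response means for one lesion.

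**The concern.** The verdict counts lesions that show a positive correlation. A correlation describes how two measurements vary together across several units, and one lesion is one unit. The correlation across subjects, which can be computed, appears in the same section, but the verdict is not tied to it.

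Someone must therefore decide what the rule means, and nothing in the plan makes that happen before the data are seen. The candidate meanings behave very differently when SUVmax and sst2 expression are unrelated, so a claim of association could rest on the choice of reading.

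**Working it through.** **Inputs.** From 12.4: the 50% threshold, one value of each measurement per biopsied lesion, and 64 subjects. From 12.1: 46 subjects, used only as a second illustrative size. From 3.1 and 4.2: one diagnostic specimen per subject. Error rates, power and marker distributions are not given for 12.4, so those below are assumptions.

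**Plan's own figure.** The 50% has no derivation, so there is nothing to reproduce.

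**Does the statistic exist?** r = Σ(x−x̄)(y−ȳ) / √[Σ(x−x̄)² Σ(y−ȳ)²]. With one lesion every deviation is 0, so r = 0/0, which is undefined. With two lesions r is always +1 or −1 (barring ties). The count of lesions with a positive correlation has no value.

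**Illustration: same side of a central cut (assumed reading), no association.**

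- Independent halves: X ~ Bin(n, 0.5), pass if X > n/2, so P = [1 − P(X = n/2)]/2.
- Median splits: if k lesions are high on both, 2k lesions agree. k is hypergeometric (n, n/2, n/2); pass if 2k > n/2.

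| Lesions | Independent halves | Median splits |
|---|---|---|
| 46 | (1 − 0.117)/2 = 0.44 | 0.50 |
| 64 | (1 − 0.099)/2 = 0.45 | (1 − 0.197)/2 = 0.40 |
| 100 | 0.46 | 0.42 |
| 200 | 0.47 | 0.44 |

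The drop from 0.50 to 0.40 in the last column arises because exactly 50% agreement is possible at 64 lesions but not at 46. Both columns tend toward 0.5 as lesions increase. With a real association (rho 0.36 at 46 lesions, 0.31 at 64) this reading passes 0.92 to 0.95 of the time, so under it the weakness is false positives.

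**Other readings, no association.**

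- Agreement on positivity, assuming every lesion is SUV-positive and a share q is expression-positive, 46 lesions: P(X ≥ 24), X ~ Bin(46, q), is 0.001, 0.06, 0.89 and 0.997 for q = 0.3, 0.4, 0.6 and 0.7.
- By lesion class (primary, liver, extra-hepatic), at least 2 of 3 correlations positive, classes independent: 3(0.5)³ + (0.5)³ = 0.50.

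**Replacement.** With the Fisher z approximation, the lower limit of the interval exceeds 0 when the observed rho exceeds tanh(z/√(n−3)).

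| Pairs | Two-sided 90% CI (z = 1.645) | Two-sided 95% CI (z = 1.96) |
|---|---|---|
| 30 | 0.31 | 0.36 |
| 46 | 0.25 | 0.29 |
| 64 | 0.21 | 0.25 |

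For the 90% version, simulation gives a null pass rate of about 0.05 per marker. The true rho for 80% power, tanh((1.645 + 0.842)/√(n−3)), is 0.445, 0.362 and 0.308. Simulated power at 0.44, 0.36 and 0.31 is 0.79, 0.79 and 0.80 without ties. With an assumed four-level IHC score it is 0.74 to 0.75 (levels 10/20/30/40%) or 0.62 to 0.64 (5/10/15/70%).

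**Both markers or either.** With an assumed between-marker correlation of 0 to 0.8 and the 90% version, the null pass rate is 0.002 to 0.025 if both must pass and 0.08 to 0.10 if either may. Power for both together is 0.61 to 0.73 without ties and 0.48 to 0.68 with four-level IHC.

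**12.3 against the calendar.** Section 7.0 schedules no diagnostic CT/MRI or ⁶⁸Ga PET between Cycle 1 and the 3–4 month follow-up. Under note 8, subjects who stop early go to calendar follow-up, so only those who stop after one dose have a response scan following Cycle 1 alone. Section 11.1 defines target response on a sum of diameters and non-target status for the disease overall, not for one lesion.

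**The case against.** The strongest reply is that 12.4 already promises a table and an ordinary correlation, so interpretable results will be reported whatever happens to the 50% sentence. No dosing, safety or primary decision uses it, and one clarifying sentence might do. The limited scope is right. But a stated decision rule that has no value still needs replacing, because the computable correlation is not what the verdict uses.

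Four stronger inferences are tempting, and the documents do not support them.

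- *The plan has a 40–50% false-positive rate.* That belongs to one assumed reading; the documents give no central cut. Section 5.1 item 3 requires at least one target lesion shown by PET to express receptors, so agreement on positivity is at least as plausible, and it gives rates from near 0 to near 1.
- *The verdict contains a three-way conflict over markers.* The verdict sentence joins RNA and receptor protein with *and*, which fits *both* in hypothesis 4. The *either* in 12.4 concerns prediction of response, and *and/or* there can be read as tissue availability. The real mismatch is mainly with *or* in 4.2.
- *The sample-size conflict undermines this rule.* Sections 12.4 and 8.2 use 64 subjects, whereas 12.1 says "If 24 or more responses are observed in the total of 46 subjects". That is a separate defect of the primary design; a share-of-lesions rule needs no fixed N.
- *Section 12.3 will confirm false positives.* That follows only if stable disease, which 12.1 counts as efficacy, is carried over to single lesions; 12.3 does not say so. Otherwise unchanged lesions simply stay unconfirmed. The Comparator trial's own scans fall under a protocol not provided here.

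It is also fair to say that Spearman, the error rate and one pair per subject are choices the plan does not dictate, and that hypothesis 4 does not require the SUV to come from the biopsied lesion. Selecting PET-positive subjects may also narrow the SUV range, which the power figures ignore.

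**Conclusion.** The verdict rule in 12.4 is wrong as written. That conclusion needs no assumption: it follows from the one-value-per-lesion table and the definition of a correlation. The size of the harm does depend on assumptions. About 0.40 to 0.50 is the null pass rate under a central-cut reading only; across readings it is essentially undetermined. The power figures rest on assumed marker distributions and on rho being a true Spearman value; if 0.36 and 0.31 are taken as Pearson correlations, power is about 0.76 to 0.77.

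A reader might infer that no correlation can be computed, or that the trial's main conclusion is at risk. Neither holds: the across-subject correlation is computable, and only secondary objectives are touched. The rule should be corrected before analysis. The 12.3 point is minor and is mostly missing detail, apart from the Cycle 1 limb.

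**What to change.** **12.4.**

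1. Delete the 50% rule and tie the verdict to the correlation already planned. Use one pair per subject: SUVmax of the biopsied lesion on the entry ⁶⁸Ga PET, where that lesion is still present and imaged, against sst2 qPCR and, separately, IHC. Keep the all-lesion table as description.
2. Report the number of pairs and Spearman rho with an interval that matches the decision. Choose in advance either a two-sided 90% or a two-sided 95% CI, with the lower limit above 0 required. Mixing them invites dispute: at 64 pairs, an observed rho of 0.22 has a one-sided 95% lower bound of 0.013, but a two-sided 95% CI of −0.03 to 0.44.
3. State whether both markers must pass, as 3.1 and the verdict sentence suggest, and reconcile this with 4.2.
4. Label the response-prediction aim as exploratory, with no verdict.

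**12.3 (minor).** Reconcile the Cycle 1 limb with the calendar, and state that an unchanged lesion does not confirm true positivity.

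**Cost.** Wording only, with no added visits, scans or tissue: 5.1 item 6 already requires archival tissue. Pairs will still be limited by sample availability and by lesions removed before PET. The claim becomes harder to meet, power falls with tied IHC scores or when both markers must pass, and some 12.3 lesions will stay indeterminate.

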13.0 Study Drug

13.1 ^{90}Y -DOTA-tyr³-Octreotide (^{90}Y -DOTATOC); IND# 61,907

13.1.1 Chemistry, Manufacturing and Control

Peptide Receptor Radionuclide Therapy (PRRT) requires a peptide conjugate that consists of the peptide receptor ligand as the targeting moiety and a chelator to bind the radionuclide as shown in Figures 1 and 2. [^{90}Y]Yttrium-DOTA-tyr³-Octreotide (^{90}Y -DOTATOC) consists of the targeting peptide tyr³-octreotide which is conjugated to the chelating moiety (DOTA) to bind the radionuclide ([^{90}Y]Yttrium). [^{90}Y]Yttrium-DOTA complexes are extremely stable³⁶.

The manufacture of ^{90}Y -DOTATOC will be conducted in the University of Iowa Nuclear Medicine Radiotherapeutics Laboratory. At least two technical personnel, one of whom has a postgraduate degree

(MS, PharmD, MD, or PhD) will be present during manufacture and quality control procedures to confirm adherence to standard operating procedures and release criteria. Reagents and supplies used for the preparation of ⁹⁰Y-DOTATOC are received and inspected per specification sheets and accepted or rejected. Accepted reagents and supplies are labeled with appropriate expiration dates, initialed, assigned identification numbers and then stored in specified locations in the Radiotherapeutics Laboratory.

Manufacture:

The starting material, DOTA-tyr³-Octreotide (DOTATOC), is manufactured under GMP conditions and is obtained commercially with appropriate certificate of analysis documentation. Manufacturing of ⁹⁰Y-DOTATOC will be performed using a synthesis unit specifically designed for this purpose ModularLab PharmTracer from Eckert & Zeigler, Berlin, Germany. The system utilizes a purpose-built, disposable, GMP-certified (sterile, pyrogen-free) cassette that is snapped into place on the synthesis unit. Computer control manages the flow of reagents for radiolabeling, purification, and transfer of the product to the final product vial via a hydrophilic PVDF sterilizing 0.22 µm filter. A new cassette is used for each preparation and preparations are usually used for a single patient study.

The final product collection vial is labelled with the batch number and other relevant information (see section 13.1.2 Labeling). The vial is weighed, then prefilled under aseptic conditions with sterile isotonic saline for injection containing ascorbic acid. This solution acts as a diluent and the ascorbic acid as an agent to aid in prevention of radiolysis of the final product. Ascorbic acid 10-50 mg, typically 50 mg for the high radioactivity runs, is dissolved in 1 mL ultrapure water and this is added to a 100 mL bag of sterile isotonic saline. After thoroughly mixing, 84 mL is removed with a sterile syringe and passed through the sterilizing filter into the final product collection vial. When the reaction product is added later in the process (~ 16 mL solution) the solution will be close to 100 mL. This volume, in this vial, gives a finely defined geometry for accurate radioactivity dose measurement.

GMP grade [⁹⁰Y]Yttrium chloride, measured against a NIST standard, is purchased commercially (e.g., Perkin-Elmer) for each manufacturing procedure³⁷. The received [⁹⁰Y]Yttrium chloride radioactivity (typically, 50 – 250 mCi) is calibrated to expected time of start of synthesis. Prior to synthesis the amount of received radioactivity is confirmed with the dose calibrator in the Radiotherapeutics Laboratory. The PharmTracer system transfers the [⁹⁰Y]Yttrium chloride using the ascorbate buffer (typically, 50 mg ascorbic acid in 1.5 mL ultrapure water) directly to a reaction vessel. The ascorbic acid serves not only as a buffer but also as an aid in prevention of radiolysis. The reaction vessel contains DOTATOC precursor dissolved in ultrapure water. To achieve maximum radiolabeling and high specific activity, the amount of precursor is restricted to the range 50-200 micrograms, typically 115 µg. The reaction mixture is heated to 95 °C for 25±5 minutes. The product is purified by passing the diluted solution (approximately 2-3 mL) through a solid phase extraction (SPE) C-18 cartridge, which retains the ⁹⁰Y-DOTATOC while allowing any remaining free [⁹⁰Y]Yttrium to pass through the column into the waste vial. The C-18 cartridge is rinsed with isotonic saline for injection to remove any residual free [⁹⁰Y]Yttrium, followed by elution of ⁹⁰Y-DOTATOC with 47.5% ethanol in water (2 mL), followed by isotonic saline (14 mL), directly through a sterile 0.22 micron membrane filter into the final product collection vial. The final product collection vial, containing ~100 mL of solution, is then agitated to give a homogenous solution of product suitable for quality control sampling and final release measurements.

Small aliquots (total 1.5 – 2 mL) are then taken for quality control testing and the product line and vent filter are removed. The final product collection vial is weighed and the contained radioactivity measured and recorded on the master batch sheet that then translates to the final product label. Radiochemical yields of >90% (uncorrected for decay) are routinely achieved. The final sterilization filter is retained for a QC pressure test to ensure filter integrity. The production process requires approximately 3 hours to complete.

Quality Control:

The QC process takes approximately 1.5 hours to complete. The quality control tests are performed and compared to release criteria prior to release of the final product as shown in Table 1 below.

Table 1. Analytical Specifications for ⁹⁰Y-DOTA-tyr³-Octreotide (⁹⁰Y-DOTATOC)

Test	Release Criteria
Appearance	Clear and no visible impurities
Filter Test	>1 bar from 2 bar overpressure at 1 minute
pH	3.0 – 7.0
Radiochemical Purity	>90%
Endotoxin	Pass gel clot tests (sample & positive control)

Appearance: Any visible cloudiness or precipitate will disqualify the product for human use.

Filter Test: A filter pressure test is conducted by applying pressure to the sterilizing filter at 2 bar inert gas (nitrogen or argon) and monitoring the leak rate for 1 minute to ensure the integrity of the filter used for final product sterilization. The system pressure should be greater than 1 bar (100 kPa, 15 psi) above atmospheric pressure after 1 minute of terminating gas supply overpressure. In the unlikely event that the filter pressure test fails, the product may be re-filtered with a fresh sterile filter under aseptic conditions with all the quality control tests being conducted on samples of the newly filtered material.

pH: The pH of the final product is measured by spotting pH paper.

Radiochemical Purity: The radiochemical purity of the final product is determined on a reverse phase high pressure liquid chromatography (HPLC) system equipped with a radiation detector, using a C18 reverse phase column and mobile phase of 0.1% TFA in water (mobile phase A) and acetonitrile (mobile phase B). Using this column and mobile phase system, free Y-90 will elute with the void volume of the column while ⁹⁰Y-DOTATOC will be retained for a significant time on the column and the two species can be differentiated by their differences in retention time. Radiochemical purity is determined by integration of the ⁹⁰Y-DOTATOC peak at a known retention time (7.8±0.5 min) and comparison to any peaks of trace free Y-90 and degradation peptides that may be present. This determination will be conducted by senior technical personnel.

Bacterial Endotoxins: Samples of final product will be tested using the limulus amoebocyte lysate (LAL) gel-clot test. If either the positive control or product fails in the LAL gel-clot test, the entire test will be repeated in triplicate. Failure of any one of the triplicate gel clot tests will disqualify the product for human use.

Sterility: Tryptic Soy Broth (TSB) and Fluid Thioglycollate Media (FTM) are inoculated with a 0.25 mL sample each of final product, incubated (TSB at room temp, FTM at 32° C) and checked for growth during the following 14 days. At the completion of the sterility test, the batch record is completed and filed. This test will not be complete at the time of administration of the product. If any product fails this test after administration of the product to a patient, that patient will be contacted to ask about any symptoms and treated if clinically indicated. An investigation of the source of contamination will be conducted and further patient studies terminated until the source identified and rectified.

Expiration date: The product expires in 48 hrs. If product will be used later than 24 hours after production, a second small sample will be obtained from the product vial and re-examined by HPLC. If radiochemical purity is <90%, the product will be declared expired and will not be administered to any patient.

Table 2 demonstrates the Quality Control testing on three successive productions of ⁹⁰Y-DOTATOC at the University of Iowa. Each production was performed according to the standard operating procedure described herein using 115 µg DOTATOC and 200±10 mCi Y-90. Detailed batch records and HPLC chromatograms are attached in a separate Chemistry, Manufacturing and Control document.

Table 2. Quality Control Measurements on Three Successive Production Runs for ⁹⁰Y-DOTATOC Manufactured at University of Iowa

	1/13/2015	1/15/2015	1/21/2015
Yield	180.8 mCi	192.8 mCi	205.0 mCi
Radiochemical Purity	97%@time zero	96%@time zero	100%@time zero
Appearance	Clear	Clear	Clear
pH	5.0	5.0	5.0
Sterility	Pass@14 days	Pass@14 days	Pass@14 days
Endotoxin	Pass	Pass	Pass
Expiration Date	Pass all release criteria @ 48 hrs	Pass all release criteria @ 48 hrs	Pass all release criteria @ 48 hrs

